9.2.2. Analysis of Secondary Endpoints

The efficacy variables are:

• Change from baseline in the Total Motor Score (TMS) assessment of the Unified Huntington Disease Rating Scale (UHDRS) after 6 and 12 months of treatment.

- Change from baseline in the Total Maximum Chorea (TMC) score of the UHDRS after 6 and 12 months of treatment.
- Clinical Global Impression-Improvement score after 6 and 12 months of treatment.

[figure not shown]
Descriptive statistics (n, mean, standard deviation, median, minimum and maximum) and 95% confidence interval will be provided to summarize results for the baseline and change from baseline values by visit. A two-sided, paired *t*-tests at the 5% level of significance will also be used to summarize results. Baseline is defined as the final visit (Week 26) in the preceding double-blind study A8241021.

Clinical Global Impression-Improvement score after 6 and 12 months of treatment will be evaluated with descriptive statistics that includes n, mean, standard deviation (SD), median, minimum, and maximum. A two-sided, one-sample *t*-tests at the 5% level of significance will be applied to evaluate results.

Missing values will be imputed using last observation carried forward (LOCF) approach. Sensitivity analysis of the secondary variables using only observed cases (no imputation) will be performed to support the robustness of the conclusions drawn from the LOCF approach.

Exploratory analysis: The mean rates of change of TMS and TMC during the double-blind period (Week 0-26) will be compared with the mean rates of change in the open label period. A two-sided, paired t-tests at the 5% level of significance will be used to summarize results.

Data for efficacy endpoints will be tested for normality assumption. If normality assumption is substantial violated, appropriate variable transformations or non-parametric tests may be performed.

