7.9.1. Unified Huntington's Disease Assessment Scale (UHDRS) – TMS, CCI

In this study four subscales of the UHDRS will be administered to the subject by a trained certified rater from the site investigational staff (clinician): the Total Motor Score (TMS),

CCI

The UHDRS is a clinical rating scale which has been developed by the Huntington Disease Study Group (HSG) to provide a uniform assessment of the clinical features and course of HD.³³ The UHDRS scale has undergone reliability and validity testing and has been used as a major outcome measure in controlled clinical trials and observational studies.³⁴ The components of the full UHDRS assess motor function, cognition, behavior and functional abilities.

The total motor score (TMS) will be recorded from study A8241021 at Baseline Day 1 (V2) visit, and will be administered at each study visit from Week 2 (V3) to Month 12 (V8) and in case of early termination.

The TMS assesses motor features of HD with standardized ratings of oculomotor function, dysarthria, chorea, dystonia, gait, and postural stability. Some items (such as chorea and dystonia) require grading each extremity (face, bucco-oral-lingual, and trunk) separately. Eye movements require both horizontal and vertical grades. The total motor impairment scores is the sum of all the individual motor ratings, with higher scores indicating more severe motor impairment than lower scores.

The Total Maximum Chorea (TMC) is a subset of the TMS assessment. It is composed of the scoring of 7 chorea assessments (face, orobuccolingual, trunk, right and left upper extremities, right and left lower extremities). Each assessment is rated from 0 to 4 (absent to prolonged). The TMC score can be derived from the TMS score at visits at which the TMS is collected.

Administration and scoring guidelines will be provided to the investigator site during rater training sessions prior to initiation of the study.

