6.8. Efficacy Endpoint(s)

Secondary Endpoints:

- *Change from baseline in the Total Motor Score (TMS) assessment of the Unified Huntington Disease Rating Scale (UHDRS) after 6 and 12 months of treatment.* The score decreases indicate improvement.
- *Change from baseline in the Total Maximum Chorea (TMC) score of the UHDRS after 6 and 12 months of treatment.* The score decreases indicate improvement.
- *Clinical Global Impression-Improvement score after 6 and 12 months of treatment.* The score decreases indicate improvement.

CCI [REDACTED] :

CCI [REDACTED] :

- CCI [REDACTED]

CCI [REDACTED] :

- CCI [REDACTED]

- CCI [REDACTED]

CCI [REDACTED] :

- CCI [REDACTED]

CCI [REDACTED] :

- CCI [REDACTED]

- CCI [REDACTED]
- CCI [REDACTED]

CCI [REDACTED]:

- CCI [REDACTED]
- CCI [REDACTED]
- CCI [REDACTED]
- CCI [REDACTED]
- CCI [REDACTED].

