7. HANDLING OF MISSING VALUES

For the analysis of safety endpoints, the sponsor data standard rules for imputation will be applied.

For scales used in this study (eg, UHDRS), no missing response will be allowed in the study. A query will be sent to the site if there is missing response.

Concentrations below the limit of quantification

In all data presentations (except listings), concentrations below the limit of quantification (BLQ) will be set to zero. (In listings BLQ values will be reported as “<LLQ”, where LLQ will be replaced with the value for the lower limit of quantification).

Deviations, missing concentrations and anomalous values

In summary tables and plots of median profiles, statistics will be calculated having set concentrations to missing if 1 of the following cases is true:

1. A concentration has been collected as ND (ie, not done) or NS (ie, no sample);
2. A deviation in sampling time is of sufficient concern or a concentration has been flagged anomalous by the pharmacokineticist.

Note that summary statistics will not be presented at a particular time point if more than 50% of the data are missing.

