8. STATISTICAL METHODOLOGY AND STATISTICAL ANALYSES

8.1. Statistical Methods

The Safety population will be used in the analyses of the safety data. The FAS analysis set will be utilized for efficacy endpoints.

All efficacy endpoints will be summarized descriptively at each visit for all subjects as well as separated by three groups (ie, from PF 20mg, from PF 5mg, and from Placebo). 90%CI will be provided for the mean. Plots with the mean over time with 90%CI will be generated for all subjects as well as by three different groups.

Baseline and change from baseline for each efficacy endpoints will also be summarized descriptively at each visit for all subjects as well as separated by three groups. Plots with mean change from baseline over time with 90%CI will be generated for all subjects as well as by three different groups.

Due to the unexpected termination of the study, any early termination visits (ET), which occurred on and after Dec. 16th, 2016, will not be included in the summary tables and plots. These data will be listed only.

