8.2. Statistical Analyses

8.2.1. Analysis of Secondary Endpoints

The efficacy variables are:

- Change from baseline in the Total Motor Score (TMS) assessment of the Unified Huntington Disease Rating Scale (UHDRS) after 6 and 12 months of treatment.
- Change from baseline in the Total Maximum Chorea (TMC) score of the UHDRS after 6 and 12 months of treatment.

- Clinical Global Impression-Improvement score after 6 and 12 months of treatment.

[figure not shown]
Descriptive statistics (n, mean, standard deviation, median, minimum and maximum) and 90% confidence interval will be provided to summarize results for each visit. The baseline and change from baseline values will be summarized as well by visit. A two-sided, paired *t*-tests at the 10% level of significance will also be used to summarize results. The paired *t*-tests will be done on all subjects and on three different groups. Baseline is defined as the final visit (Week 26) in the preceding double-blind study A8241021.

Clinical Global Impression-Improvement score after 6 and 12 months of treatment will be evaluated with descriptive statistics that includes n, mean, standard deviation (SD), median, minimum, and maximum. A two-sided, one-sample *t*-tests at the 5% level of significance will be applied to evaluate results.

Plots will be generated for mean change from baseline as well as mean over time as described in [Section 8.1](#).

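### The SAP's Month 6 and Month 12 tests of TMS and TMC use only subjects seen at that visit, with no visible missing-data sensitivity analysis; a repeated-measures model on visits already collected would be safer

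*Protocol*

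**What the plan says.** **Protocol.** Section 9.2.2 sets the main rule for the secondary efficacy variables: "Missing values will be imputed using last observation carried forward (LOCF) approach". It adds a check: "Sensitivity analysis of the secondary variables using only observed cases (no imputation) will be performed". The introduction to section 9 lets the SAP change these plans; only major changes to the primary endpoint or its analysis need an amendment.

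**SAP.** The efficacy table in 8.5 lists paired t-tests for TMS and TMC and a one-sample t-test for CGI-I. It names no covariates and marks missing data as excluded in all three rows. Section 8.2.1 adds: "The paired *t*-tests will be done on all subjects and on three different groups". It mentions neither LOCF nor a sensitivity analysis. Section 7 says "For scales used in this study (eg, UHDRS), no missing response will be allowed in the study", which deals with unanswered items and not with missed visits. Section 8.1 removes late exit data: "any early termination visits (ET), which occurred on and after Dec. 16th, 2016, will not be included in the summary tables and plots".

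**Data available.** Under Protocol 7.9.1 the TMS "will be administered at each study visit from Week 2 (V3) to Month 12 (V8) and in case of early termination". That is six post-baseline visits (Weeks 2 and 4, Months 3, 6, 9 and 12), and TMC can be derived wherever TMS is collected. SAP 8.1 uses all of them descriptively: "Baseline and change from baseline for each efficacy endpoints will also be summarized descriptively at each visit for all subjects".

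**The concern.** The secondary hypothesis in SAP 4.1 is that mean change in TMS and TMC is below 0, and SAP 6.8 gives the direction: "The score decreases indicate improvement". There is no control arm. If subjects whose motor score worsens are more likely to be absent at Month 6 or Month 12, those still present have a better mean than the whole group. The test then leans toward the result it is looking for.

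The documents make such dropout plausible, though they do not show it. TMS includes dystonia ratings. Protocol Appendix 1 predicts that up to 10% of subjects titrated to 20 mg may have extrapyramidal events needing intervention, and its Figure 2 allows for withdrawal when such an event does not resolve.

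The protocol's two-method comparison would have given some warning of this. The visible SAP has nothing in its place, and no model uses a subject's earlier scores to inform the Month 6 or Month 12 mean.

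**Working it through.** **No planned figure to reproduce.** The 260 subjects are a roll-over ceiling (Protocol 9.1). Neither document gives an SD, effect size, dropout rate or reasons for dropout. Every input below except the visit days and the 260 is therefore an assumption.

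**Step 1: bias by simulation** (400,000 subjects per scenario).
- Visits: Days 14, 28, 91, 182, 273 and 365.
- Change from baseline: random slope plus residual error. Slope SD is 6 points per year and residual SD is 4, so the SD of 12-month change is √(6² + 4² + 4²) = √68 ≈ 8.2.
- True mean 12-month change: 0, +2 or +4 points.
- Missing at Month 12: 15%, 30% or 45%.
- Dropout: unrelated to TMS; more likely after a worse last observed TMS (missing at random, MAR); or more likely with a worse unobserved TMS (MNAR).
- Estimators: observed cases (SAP), LOCF (protocol), and a likelihood estimate from all visits (sequential regression, equivalent to maximum likelihood for monotone MAR data).

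Month 12 bias in points (negative is toward improvement), for 15% / 30% / 45% missing:

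| Dropout | Observed cases | Likelihood, all visits |
|---|---|---|
| Unrelated to TMS | 0 / 0 / 0 | 0 / 0 / 0 |
| MAR | -0.7 / -1.5 / -2.4 | within 0.02 of 0 |
| MNAR | -1.0 / -2.0 to -2.1 / -3.1 to -3.3 | -0.5 / -1.0 / -1.7 |

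At Month 6 the observed-case bias is smaller: about -0.2 to -0.8 under MAR and -0.3 to -1.3 under MNAR.

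**Step 2: LOCF as a reference.** With a true worsening of +2 or +4 and dropout unrelated to TMS, LOCF is off by -0.2 to -1.15 points at Month 12. Over all the true means simulated, it is off by +0.6 to -0.5 under MAR and by -0.3 to -2.0 under MNAR. It is not a clean benchmark.

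**Step 3: chance of a false improvement finding, if the true change is 0.** Normal approximation: P = Φ(|bias| / SE − z), with SE = 8.2 / √n and n the share of 260 still observed. For 30% missing, n = 0.70 × 260 = 182, SE = 8.2 / √182 = 0.608, and 1.5 / 0.608 = 2.47.
- Two-sided 5% (same cut-off as one-sided 2.5%): Φ(2.47 − 1.96) ≈ 69%.
- Two-sided 10%: Φ(2.47 − 1.645) ≈ 80% (79.5%).

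For 15% missing (n = 221, SE 0.552, bias 0.7) the two figures are about 24% and 35%. For 45% missing (n = 143, SE 0.686, bias 2.4) they are about 94% and 97%. Both cut-offs are shown because SAP 4.2 uses one-sided 2.5% and SAP 8.2.1 uses two-sided 10% for TMS and TMC.

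**Step 4: when there is true worsening.** Take +4 points, 30% missing and MAR. The observed mean is about 4.0 − 1.5 = +2.5. The worsening is understated, but no improvement is declared.

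**Step 5: termination only.** A separate simulation used N = 200, slope SD 4, residual SD 3.5, and 40% remaining at Month 12 for reasons unrelated to TMS. The likelihood estimate has about 25% less variance at Month 12 (variance ratio 0.75). Observed cases are unbiased there too.

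**The case against.** Most of the case against a stronger claim stands.

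- **A breach of the protocol.** A reader might infer one. Section 9 permits the SAP to modify secondary analyses, and the method kept is the protocol's own sensitivity analysis.
- **Loss of LOCF as the defect.** LOCF carries early values forward in a progressive disease and can itself hide worsening (Step 2). Restoring it would not solve the problem.
- **A completers-only analysis.** The SAP rule is available cases at each visit. The Month 6 test keeps subjects who leave later; only Month 12 comes close to completers.
- **Intermediate visits thrown away.** They are summarised and plotted at each visit, pooled and by prior-dose group. They are unused only for the Month 6 and Month 12 estimates.
- **The paired t-test as the only analysis.** This cannot be established, because SAP 3.1, 6.12, 8.2.2 and 8.4 are redacted. One can say only that no other analysis is visible.
- **Bias as a fact.** The one documented cause of widespread missing data is the unexpected study termination, which may be unrelated to TMS. In that case observed cases are unbiased.

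It is also fair that these are secondary endpoints in an uncontrolled extension, and that a repeated-measures model is unbiased only under MAR. Under MNAR it roughly halves the bias and does not remove it. What remains is that the planned robustness comparison is gone, and that data already collected could protect the estimates at little cost.

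**Conclusion.** The point holds as a conditional weakness and a cheap improvement; it is not an error in the primary analysis, which concerns safety. If worsening subjects are more likely to leave, the SAP's estimates are too favourable, by the Month 12 and Month 6 amounts in Step 1. The usual consequence is understated worsening. A false improvement finding needs two conditions together: informative dropout and no true worsening. The documents establish neither, so they do not support reading the 69% or 80% as this trial's actual error rate. If missingness is unrelated to TMS, the only loss is precision. All sizes rest on the assumed slopes, SDs and dropout models above.

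**What to change.** In SAP 8.2.1 and 8.5:

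1. Analyse TMS and TMC by MMRM on all post-baseline visits included under SAP 8.1. Terms: baseline score, visit, prior-dose cohort, and cohort by visit. Use an unstructured covariance, with a simpler structure named in advance if the model does not converge.
2. Report the estimates for each cohort at Months 6 and 12, and an overall change weighted by the observed cohort sizes, all with confidence intervals.
3. Keep the observed-case paired t-test as a sensitivity analysis.
4. Tabulate reasons for missing data by visit, and add one simple MNAR analysis in which imputed values are shifted by a stated delta.
5. Leave CGI-I as planned. It is rated only at Months 6 and 12 and at early termination, so there are no intermediate ratings to borrow from.

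The SAP should also say how early-termination scores retained under 8.1 enter the model, because the Appendix 3 windows leave gaps (for example Days 99 to 167).

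The cost is SAP wording, one standard model and one table; no new data are needed. The drawback is reliance on missing at random, which is why the result should stand beside the observed-case and MNAR results.

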9.5. Safety Analysis

Adverse events, ECGs, blood pressure, pulse rate and safety laboratory data will be reviewed and summarized on an ongoing basis during the study to evaluate the safety of subjects. Any clinical laboratory, ECG, BP, and PR abnormalities of potential clinical concern will be described. Safety data will be presented in tabular and/or graphical format and summarized descriptively, where appropriate.

Physical examination and neurologic examination information collected during the course of the study will not be captured for inclusion into the study database, unless otherwise noted. However, any untoward findings identified on physical and/or neurologic examinations conducted after the administration of the first dose of study medication will be captured as an adverse event, if those findings meet the definition of an adverse event. Demographic data collected at Screening will be included in the study database. C-SSRS responses will be mapped onto the C-CASA scale, and the frequency distribution of the C-CASA scores (pre-dose/post-dose) will be reported. No hypotheses associated with the C-SSRS or C-CASA scales will be tested.

9.5.1. Electrocardiogram (ECG) Analysis

Changes from baseline for the ECG parameters QT interval, heart rate, QTc interval, PR interval and QRS interval will be summarized by treatment and time. The number (%) of subjects with maximum post-dose QTc values and maximum increases from baseline in the following categories will be tabulated by treatment:

Table 7. Safety QTc

	Borderline (msec)	Prolonged (msec)
Absolute Value	>=450 - <480	>=480
Absolute Change	30-<60	>=60

In addition, the number of subjects with corrected and uncorrected QT values >=500 msec will be summarized.

9.6. Interim Analysis

No interim analysis will be performed in the study.

9.7. Data Monitoring Committee

This study will use an External Data Monitoring Committee (E-DMC).

An independent unblinded External DMC consisting of experts in movement disorder, hematology/clinical trial safety monitoring, and statistics will evaluate the safety of the trial on an ongoing basis. Further detail on the composition and responsibility of the Data Monitoring Committee is outlined in a separate DMC charter. The E-DMC will make recommendations related to the study continuation based on their safety review as described in the PDE10 program level DMC Charter. For purposes of internal decision-making, an Executive Steering Committee (ESC) may be identified to liaise with the E-DMC to review E-DMC recommendations. No members of the ESC will be involved in the day to day conduct of the study. The results of the DMC review will not be shared with the study team, except for the key outcome ("Stop for unacceptable safety findings", or "Continue"). Further detail on the composition and responsibility of the E-DMC and ESC will be outlined in a separate DMC charter.

The program level external DMC was established in May 2013 for all PDE10 studies. The DMC charter gets amended for addition of each new interventional protocol with PF-02545920. The E-DMC meets on a regular basis and will evaluate this trial safety as soon as possible after the first approximately 20 subjects have completed Month 6 (V6), and then periodically at least twice a year thereafter. The sponsor may request an *ad hoc* meeting earlier, and/or more frequent review of safety data by the E-DMC, should potential safety signals of concern arise from blinded medical review of adverse events and other safety data by the Pfizer medical monitor. The timing of the E-DMC reviews may also be slightly adjusted to align with scheduled safety analysis for other studies, as specified in the DMC Charter. More information on the frequency of the E-DMC reviews will be included in the DMC Charter.

The E-DMC will be responsible for external monitoring of the safety of subjects in the study according to the charter. Prior to every scheduled E-DMC safety review the E-DMC members will receive an unblinded data package that will include all available safety data. Additionally, serious adverse event (SAE) case reports and drug related discontinuations will be communicated to the E-DMC on an ongoing basis, as soon as the sponsor is notified. The recommendations made by the E-DMC to alter the conduct of the study will be forwarded to

Pfizer for final decision. Pfizer will forward such decisions, which may include summaries of aggregate analyses of endpoint events and of safety data that are not endpoints, to regulatory authorities, as appropriate.

10. QUALITY CONTROL AND QUALITY ASSURANCE

During study conduct, Pfizer or its agent will conduct periodic monitoring visits to ensure that the protocol and Good Clinical Practices (GCPs) are being followed. The monitors may review source documents to confirm that the data recorded on CRFs are accurate. The investigator and institution will allow Pfizer monitors/auditors or its agents and appropriate regulatory authorities direct access to source documents to perform this verification.

The study site may be subject to review by the institutional review board (IRB)/ethics committee (EC), and/or to quality assurance audits performed by Pfizer, or companies working with or on behalf of Pfizer, and/or to inspection by appropriate regulatory authorities.

It is important that the investigator(s) and their relevant personnel are available during the monitoring visits and possible audits or inspections and that sufficient time is devoted to the process.

11. DATA HANDLING AND RECORD KEEPING

11.1. Case Report Forms/Electronic Data Record

As used in this protocol, the term CRF should be understood to refer to either a paper form or an electronic data record or both, depending on the data collection method used in this study.

A CRF is required and should be completed for each included subject. The completed original CRFs are the sole property of Pfizer and should not be made available in any form to third parties, except for authorized representatives of Pfizer or appropriate regulatory authorities, without written permission from Pfizer.

The investigator has ultimate responsibility for the collection and reporting of all clinical, safety, and laboratory data entered on the CRFs and any other data collection forms (source documents) and ensuring that they are accurate, authentic/original, attributable, complete, consistent, legible, timely (contemporaneous), enduring, and available when required. The CRFs must be signed by the investigator or by an authorized staff member to attest that the data contained on the CRFs are true. Any corrections to entries made in the CRFs or source documents must be dated, initialed, and explained (if necessary) and should not obscure the original entry.

In most cases, the source documents are the hospital's or the physician's subject chart. In these cases, data collected on the CRFs must match the data in those charts.

In some cases, the CRF, or part of the CRF, may also serve as source documents. In these cases, a document should be available at the investigator's site as well as at Pfizer and clearly

identify those data that will be recorded in the CRF, and for which the CRF will stand as the source document

